9.4 STATISTICAL ANALYSES

9.4.1 GENERAL APPROACH

Means, medians, standard deviations (SDs), coefficients of variation (CVs), and relative frequencies will be used to describe the study sample's characteristics and to report the observed imaging measurements. 95% CIs will be constructed for measures of precision. Log transformations of imaging measurements will be performed, as appropriate.

9.4.2 ANALYSIS OF THE PRIMARY EFFICACY ENDPOINT(S)

$RDC_{diff-day, diff-operator}$ will be estimated as follows:

$$\widehat{RDC}_{diff-day,diff-operator} = 2.77 \times \sqrt{\sum_{j=1}^5 \sum_{i=1}^{N_j} (Y_{1ij} - Y_{2ij})^2 / 2\bar{Y}_{ij}^2 N}$$

where Y_{1ij} is the biomarker measurement at timepoint 1 and Y_{2ij} is the biomarker measurement on the same scanner j by a different operator at timepoint 2 for the i^{th} participant. \bar{Y}_{ij} is the mean of Y_1 and Y_2 for participant i for scanner j . N_j is the total number of participants per scanner, and N is the total number of observations. The 95% upper bound for $RDC_{diff-day,diff-operator}$ will be constructed as follows:

$$\widehat{RDC} \sqrt{\frac{N}{\chi_{N,\alpha}^2}}$$

where $\chi_{N,\alpha}^2$ is the α th percentile of the chi square distribution with N degrees of freedom and α is 0.95. A bootstrap 95% CI will also be constructed for RDC , where sampling with replacement will be performed at the subject level. If the upper 95% confidence bound is < 0.35 ($< 35\%$), then it will be concluded that the biomarker meets the prespecified precision criterion.

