Participants will be consecutively assigned to their corresponding category until the category is closed (reaches maximum of 11). Once a category is closed at a given site, participants will no longer be enrolled into that category at that site.

Each participant will undergo ultrasound imaging at Visit 1 (by operator 1) and at Visit 2 (by operator 2), separated by 1 to 7 days. The 7-day window for Visit 2 is selected to allow flexibility in scheduling while helping to ensure that there is no substantial biological change in the interim. Ultrasound exams at Visits 1 and 2 will be performed at about the same time of day (target is ± 2 hours) and with identical fasting and other preparation instructions. For each visit, each participant will be assigned to three of the five ultrasound scanners plus VCTE. As shown in the Schema (**Section 1.2**), for Visit 1, two of the three ultrasound exams will be repeated; the third ultrasound exam and the VCTE exam will be performed once. For Visit 2, the third ultrasound exam and the VCTE exam will be repeated; the other two ultrasound exams will be performed once. The selection of exams to be repeated will be based on a block assignment strategy to ensure an approximately equal number of scans are performed by each ultrasound system, in addition to VCTE. Thus, each subject will undergo a total of six exams at each of their two visits, for a total of 12 exams across both visits. For the repeated exams, subjects will get off the table with a short break (target about 5 minutes) before getting back on the table. Subjects will not be required to leave the room. The machine will not be turned off and powered up again to save time

Ultrasound operators will follow the acquisition procedures outlined in the imaging manual. The imaging manual will address patient positioning, image acquisition and quality control with scanning protocol input from the relevant ultrasound vendors. Additional investigational ultrasound data may be acquired, including with use of non-FDA-approved vendor proprietary software.

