9.2 SAMPLE SIZE DETERMINATION

The following assumptions were made in determining sample size for the primary study objective:

1. Repeat measurements on the same participant follow a normal distribution.
2. $RDC_{\text{diff-day, diff-operator}}$ is in the range of 20-30% (wCV of 7.2-10.8%).
3. A balanced design is planned (i.e. equal number of participants per scanner) where the following scenarios describe the possible RDCs across the five scanners:
 - 25, 25, 25, 25, 25%
 - 24, 25, 25, 26, 27%
 - 23, 25, 25, 27, 29%
 - 23, 25, 25, 27, 30%
4. A study with 80% power is desired.

The null hypothesis for the primary study objective is $H_0: RDC_{\text{diff-day, diff-operator}} \geq 35\%$, versus the alternative hypothesis that $RDC_{\text{diff-day, diff-operator}} < 35\%$, where RDC is the reproducibility coefficient for different day and different operator. The upper 95% confidence bound for the RDC will be constructed.

A Monte Carlo simulation study was conducted to determine the sample size needed. For each simulated participant, two observations were generated from a normal distribution with the specified variance. Samples of varying size were simulated. From each sample $RDC_{diff-day, diff-operator}$ was estimated, along with its 95% CI. This process was repeated 10,000 times.

In the table below the sample size is reported such that 80% of the samples of that size met the precision qualification (i.e. upper 95% confidence bound for $RDC < 35\%$). The results suggest that by pooling across the five scanners, up to 55 independent observations are needed. With each subject scanned on three different scanners at the two time points and assuming moderate correlation between observations from the same subject ($r=0.25$), we consider the design effect to account for the clustering of the data (i.e. 3 observations/subject). The design effect is $1+(s-1)r$, where r =correlation and s =# of observation/subject, i.e. $1+(3-1)0.25=1.5$. Thus, $(55 \times 1.5)/3=27.5$ so a study with 28 total participants would provide 80% power.

For estimating the $RDC_{diff-day, diff-operator}$ of VCTE, assuming an $RDC_{diff-day, diff-operator}$ of 25%, 32 subjects provides 80% power to show that the $RDC < 35\%$. Taking into consideration the possibility of a drop-out or technical failure rate of no more than 25%, a study with 40 total participants (20 per site) is proposed.

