9.4.3 ANALYSIS OF THE SECONDARY ENDPOINT(S)

For each biomarker and each scanner, $RC_{same-day,same operator}$ will be estimated as follows:

$$\widehat{RC}_{same-day,same operator} = 2.77 \times \sqrt{\sum_{i=1}^N (Y_{1i} - Y_{2i})^2 / 2\bar{Y}_i^2 N_j}$$

where Y_{1i} is the biomarker measurement at timepoint 1 and Y_{2i} is the replicate biomarker measurement on the same scanner by the same operator at timepoint 1 for the i^{th} participant. \bar{Y}_i is the mean of Y_1 and Y_2 for participant i . N_j is the total number of participants per scanner.

For each biomarker and each scanner, $RC_{diff-day,diff-operator}$ will be estimated as follows:

$$\widehat{RC}_{diff-day,diff-operator} = 2.77 \times \sqrt{\sum_{i=1}^N (Y_{1i} - Y_{2i})^2 / 2\bar{Y}_i^2 N_j}$$

where Y_{1i} is the biomarker measurement at timepoint 1 and Y_{2i} is the biomarker measurement on the same scanner by the same operator at timepoint 2 for the i^{th} participant. \bar{Y}_i is the mean of Y_1 and Y_2 for participant i . N_j is the total number of participants per scanner.

For each biomarker and a pair of scanners, $RDC_{scanner}$ will be estimated as follows:

$$\widehat{RDC}_{scanner} = 2.77 \times \sqrt{\sum_{i=1}^{N_{j,j'}} (Y_{1i} - Y_{2i})^2 / 2\bar{Y}_i^2 N_{j,j'}}$$

where Y_{1i} is the biomarker measurement at timepoint 1 and Y_{2i} is the biomarker measurement on a different scanner for the i^{th} participant. This RDC will be estimated both with the same and different operators, and on the same and different days. \bar{Y}_i is the mean of Y_1 and Y_2 for participant i . $N_{j,j'}$ is the number of participants scanned on the scanners j and j' .

For each biomarker and each scanner, 95% upper bounds for $RC_{\text{same-day,same-operator}}$, $RC_{\text{diff-day,diff-operator}}$, and RDC_{scanner} will be constructed as follows:

$$\widehat{RC} \sqrt{\frac{N}{\chi_{N,\alpha}^2}}$$

where $\chi_{N,\alpha}^2$ is the α th percentile of the chi square distribution with N degrees of freedom and α is 0.95.

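### Each participant-device gives three readings, but the primary RDC formula uses one per visit and does not say which repeat; using both cross-visit pairings is more precise and supplies the missing rule

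*Combined protocol and SAP*

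**What the plan says.** Section 4.1 assigns each participant three of the five scanners plus VCTE. At the first imaging visit, "for Visit 1, two of the three ultrasound exams will be repeated; the third ultrasound exam and the VCTE exam will be performed once". At the second, "For Visit 2, the third ultrasound exam and the VCTE exam will be repeated; the other two ultrasound exams will be performed once". The section totals this as 12 exams per participant, six at each visit.

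Section 9.4.2 defines the primary RDC from one Y1 and one Y2 per participant and scanner, where Y2 "is the biomarker measurement on the same scanner j by a different operator at timepoint 2". It does not say which value is used when the exam was done twice at that visit. The section gives a chi-square bound on N degrees of freedom, adds a bootstrap interval resampled by participant, and applies the rule "If the upper 95% confidence bound is < 0.35" without saying which bound decides.

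Section 9.4.3 uses the repeats for the same-day, same-operator repeatability coefficient, where the second value "is the replicate biomarker measurement on the same scanner by the same operator at timepoint 1". Section 9.2 sized the study on one pair: "For each simulated participant, two observations were generated from a normal distribution with the specified variance".

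**The concern.** No participant-device has exactly one reading per visit, so the missing rule touches every pair in both primary endpoints. The analyst could take the first repeat, the second, or their mean. The first two estimate the same quantity but can give different answers. The mean estimates something smaller, because it removes part of the same-day error, and that shift favours passing the 35% criterion for automatic advancement to Stage 2.

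There is also an opportunity. The third reading carries information on the primary RDC that the formula does not use. VCTE has the least slack: 40 enrolled with 25% loss leaves 30, against the 32 given in 9.2.

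**Working it through.** **Inputs.** Exam pattern from 4.1; RDC formula, chi-square bound and 35% rule from 9.4.2; 55 observations, 28 participants, VCTE 32, 25% loss and 40 enrolled from 9.2. The share f of the between-visit variance that is same-day repeat error is not in the documents; I use 1/3, 0.5 and 0.7. The chi-square bound is taken with a lower-tail percentile (5th for one-sided, 2.5th for the upper limit of a two-sided interval).

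**1. Count.** Visit 1: 2×2 + 1 + 1 = 6. Visit 2: 2 + 2 + 1 + 1 = 6. Total 12 = 4 devices × 3 readings. At full enrolment the five scanners give 40×3×3 = 360 readings. The formula uses 40×3 = 120 pairs, that is 240 readings, and leaves 120 out.

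**2. The plan's own figures.** Simulating one reading per visit with the 9.4.2 estimator and the 2.5th percentile gives power 0.799, 0.803, 0.798 and 0.816 at 40, 45, 50 and 55 observations, so the 9.2 table reproduces. (55×1.5)/3 = 27.5, hence 28. VCTE with 32 gives 0.808 with the 5th percentile (0.690 with the 2.5th). The single-reading basis is therefore confirmed.

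**3. Gain from both pairings.** Let σa² be the day/operator variance and σe² the repeat variance, with f = σe²/(σa²+σe²). The two cross-visit differences each have variance 2σa²+2σe² and share 2σa²+σe², so their correlation is ρ = 1 − f/2. The average of the two squared differences has variance (1+ρ²)/2 times that of one, so effective N is multiplied by 2/(1+ρ²).

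| f | ρ | Effective N factor | Simulated variance ratio |
|---|---|---|---|
| 1/3 | 0.833 | 1.18 | 1.19 |
| 0.5 | 0.75 | 1.28 | 1.28 |
| 0.7 | 0.65 | 1.41 | 1.40 |

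At f = 0 the factor is 1.

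**4. What it does for VCTE** (n = 30, true RDC 25%, 5th percentile):

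| Estimator and bound | Power at f = 1/3, 0.5, 0.7 | False qualification at true 35% |
|---|---|---|
| One reading per visit, 30 df | about 78% | about 4.5% |
| Both pairings, 30 df | 80, 81, 82% | 2 to 3% |
| Both pairings, df = 30×2/(1+ρ²), ρ from the data | 84, 87, 89% | near 5% |

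The plain bound becomes conservative and absorbs most of the gain. With the 2.5th percentile, power for one reading per visit is about 66%, and for both pairings with adjusted degrees of freedom roughly 74 to 82%.

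**5. If repeats were averaged first.** The variance of the difference is 2σa²+1.5σe², so the RDC is multiplied by √(1 − f/4) = 0.957, 0.935, 0.908. At a true 35%, 90 pairs treated as independent (30 participants × 3 scanners) and the 5th percentile, false qualification rises from about 4% to about 11, 18 and 29%.

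**6. If the choice of repeat is left open.** With 30 VCTE participants at RDC 25%, choosing the first or the second repeat gives opposite pass/fail results in 18, 22 and 25% of simulated studies. Taking whichever passes raises false qualification at a true 35% from about 4.5% to 7-8%.

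**7. Bootstrap at n = 30.** With both pairings and a true RDC of 35%, a percentile bootstrap by participant (the plan does not name the type) falsely qualifies about 10 to 11% of the time at its 95th percentile and about 8% at its 97.5th.

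**The case against.** The strongest reply is that nothing is wrong with the formula. One pre-chosen reading per visit is an essentially unbiased estimate of the single-measurement RDC, and 9.2 sized the study on exactly that. This stands: a reader might infer that planned power is overstated, and it is not. The VCTE gap of 30 against 32 comes from the allowance for losses, not from the estimator.

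A reader might also infer that a third of the data is thrown away. That is true only as a count inside the primary estimator. The repeats were collected for the secondary repeatability coefficient and are used there. The information forgone for the primary RDC is 1 − 1/1.18 = 15% to 1 − 1/1.41 = 29% over the assumed range, and zero at f = 0.

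A third tempting inference is that the plan will average the repeats. No section says so, and 9.4.3 treats the second exam as a separate measurement. The inflation in step 5 shows why averaging should be excluded; it does not describe a planned analysis. It also treats clustered pairs as independent, although 9.2 assumes a within-participant correlation of 0.25.

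Finally, the gain depends on the bound. It is 1 to 4 points with the plain chi-square, and the bootstrap already in 9.4.2 is no remedy at about 30 participants because it is too liberal. Both points stand and shape the fix.

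What the reply does not answer is the missing rule. Section 9.4.7 defers additional analyses to a Statistical Analysis Plan, and a separate Image Review Charter is mentioned in 6.4, but nothing in the documents supplied says which repeat enters. Wherever else such a rule may sit, the primary analysis section should state it.

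**Conclusion.** The point holds as a missing rule plus an efficiency improvement, not as an error in the estimator or in planned power. Section 9.4.2 leaves open which repeat enters each of the 120 scanner pairs and 40 VCTE pairs planned at full enrolment. Using both pairings keeps the estimand and raises effective N by about 1.18 to 1.41. With suitably adjusted degrees of freedom, one-sided VCTE power at 30 participants and RDC 25% goes from about 78% to 84-89%, with false qualification kept near 5%.

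These sizes rest on normal errors, equal repeat variance at both visits, and f between 1/3 and 0.7, which is assumed. That both pairings are at least as precise as one, and that averaging first biases the RDC downward, holds for any f above zero. The change is worth making because the rule feeds an automatic qualification decision.

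**What to change.** In 9.4.2, for the pooled scanners and for VCTE:

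- For each participant and device, compute the squared relative difference for both cross-visit pairings, average the two, and use that average in the sum.
- State that repeat readings are not averaged before differencing.
- Take the bound from a chi-square lower-tail percentile with n×2/(1+ρ²) degrees of freedom, where ρ is the observed correlation of the two cross-visit differences. For the pooled scanners also allow for clustering within participant, for example by a design effect of the form in 9.2.
- Say which bound decides. Do not let a percentile bootstrap decide for VCTE at about 30 participants; report it as supportive.

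If this is not wanted, the minimum is to fix one reading in advance, such as the first exam at each visit.

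The cost is a few sentences and slightly more complex code, with degrees of freedom that depend on the data. No extra scans are needed.

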Secondary endpoints:

- Evaluation of pooled same-day, same-operator repeatability coefficient of ultrasound-based measurements of SWS.
- Evaluation of pooled different-scanner, same-day reproducibility coefficient of ultrasound-based measurements of SWS.
- Evaluation of same-day, same-operator repeatability coefficient of VCTE on the measurement of SWS and Young's modulus.
- Evaluation of different-day, different-operator reproducibility coefficient of VCTE on the measurement of Young's modulus.

Exploratory endpoints

- Precision and other reliability metrics of vendor- or device-specific investigational measurements of other components of NAFLD such as steatosis and possibly inflammation.

Study Population

This study will enroll patients with suspected or confirmed diagnosis of NAFLD. Based on protocol-specified FIB-4 values, about one-third are expected to have low, one-third to have intermediate, and one-third to have high likelihood of advanced fibrosis. The sample size of 40 participants was determined to provide sufficient sample to provide >80% power to qualify SWS (or equivalent) as an ultrasound (US)-based biomarker for advancement to Stage 2. The threshold for automatic qualification for advancement to Stage 2 will be an upper bound of the 95% confidence interval (CI) of the reproducibility coefficient less than 35%. Dropouts and technical failures were included in this sample size determination.

Sex: ~ 50:50 – Note- no stratification will be done based on sex

Age: ≥ 18 yrs

Demographic group: Patients with a high probability of NAFLD based on the eligibility criteria

General health status: Patients with suspected or confirmed diagnosis of NAFLD

Geographic location: San Diego, CA and Boston, MA (greater metropolitan areas)

Phase

N/A

[figure not shown]
Description of Sites/Facilities Enrolling Participants Planned facilities/participating sites enrolling participants: University of California- San Diego (UCSD) and Massachusetts General Hospital (MGH)
 Number of sites: 2

Description of Study Intervention Study will not have any therapeutic intervention. The goal of the study will be evaluating the variability of ultrasound-based measures for the diagnosis and monitoring of NAFLD/NASH.

Study Duration 12 months

Participant Duration < 1 month

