Number of Independent Observations needed for $\geq 80\%$ power as a function of the five scanners'

	$RDC_{diff-day, diff-operator}$			
RDCs across 5 scanners:	25, 25, 25, 25, 25%	24, 25, 25, 26, 27%	23, 25, 25, 27, 29%	23, 25, 25, 27, 30%
Total # independent observations	40	45	50	55

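### The two primary sample sizes use different tails for the 35% bound, and the pooled chi-square bound ignores the clustering assumed in 9.2

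*Combined protocol and SAP*

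**What the plan says.** **Tail.** The synopsis (1.1) states: "The threshold for automatic qualification for advancement to Stage 2 will be an upper bound of the 95% confidence interval" of the RDC below 35%. The hypothesis in 4.1 also uses the upper limit of the 95% CI. Sections 9.2 and 9.4.2 instead speak of an upper 95% confidence bound. No section says one-sided or two-sided. The formula in 9.4.2 uses the αth percentile of chi-square with α set to 0.95.

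**Sizes.** The table in 9.2, in the row "Total # independent observations", gives 40, 45, 50 and 55 for four scenarios of scanner RDCs; the first has all five at 25%. For VCTE, also at RDC 25%, 9.2 says that "32 subjects provides 80% power to show that the" RDC is below 35%.

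**Clustering.** Section 9.2 proceeds "assuming moderate correlation between observations from the same subject" with r = 0.25, and says "we consider the design effect to account for the clustering of the data (i.e. 3 observations/subject". The factor is 1.5, which leads to 28 participants. In the 9.4.2 bound, "N is the total number of observations", and N is also the degrees of freedom.

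**Deciding bound.** After the chi-square formula, 9.4.2 adds: "A bootstrap 95% CI will also be constructed for" the RDC, resampling subjects. The decision sentence begins "If the upper 95% confidence bound is" below 35%. It does not name either method.

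**The concern.** The 35% rule is the primary decision for both primary endpoints. The pooled table at RDC 25% and the VCTE size pose the same problem: one pair per independent unit, true RDC 25%, limit 35%, 80% power. The answers should agree, but one is 40 and the other 32. If a single rule governs both, one of the stated sizes or powers is wrong, and an estimate near the limit can pass under one tail and fail under the other.

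The second worry concerns the pooled endpoint only. The design allows for correlation among one subject's three scanner pairs, but the chi-square bound counts every pair as a full degree of freedom. If that correlation is material, the bound is too narrow and a pooled RDC of 35% qualifies more often than the nominal rate. VCTE gives one pair per subject and is not affected.

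**Working it through.** Results are given as 5% point / 2.5% point of the lower chi-square tail.

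**1. Reproducing the plan's sizes.** Inputs from 9.2 and 9.4.2: two normal values per pair, within-subject CV = RDC/2.77, the 9.4.2 estimator, and bound = estimate × √(N/χ²_{N,a}), passing if below 35%. At a common RDC of 25%, a close approximation to power is P(χ²_N < χ²_{N,a} × (35/25)²), with (35/25)² = 1.96.

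- N = 40, a = 0.025: 24.43 × 1.96 = 47.89, power 81.7%. With a = 0.05: 26.51 × 1.96 = 51.96, power 90.3%.
- N = 32, a = 0.05: 20.07 × 1.96 = 39.34, power 82.6%. With a = 0.025: 18.29 × 1.96 = 35.85, power 70.7%.

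Simulation with the plan's own estimator is slightly lower:

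| Case | N | Power, 5% point | Power, 2.5% point |
|---|---|---|---|
| 25, 25, 25, 25, 25% | 40 | 89% | 80% |
| 24, 25, 25, 26, 27% | 45 | 89% | 80.5% |
| 23, 25, 25, 27, 29% | 50 | 89% | 80% |
| 23, 25, 25, 27, 30% | 55 | 90% | 81.6% |
| VCTE, 25% | 32 | 81% | 69% |

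The table fits only the 2.5% point; at the 5% point, about 35, 35, 40 and 45 would do. VCTE fits only the 5% point; at the 2.5% point it needs about 40. The step 55 × 1.5 / 3 = 27.5, hence 28, reproduces.

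**2. The percentile in 9.4.2.** Read literally, the 95th percentile gives a multiplier below 1: 0.905 at N = 120, so estimates up to 35/0.905 = 38.7% would pass. That is not an upper bound, so the α value cannot be used as evidence for either tail.

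**3. Degrees of freedom.** A 25% loss from 40 leaves 30 completers and 30 × 3 = 90 pairs. The plan's own factor gives 90/1.5 = 60.

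| df | Multiplier | Largest passing estimate |
|---|---|---|
| 90 | 1.141 / 1.171 | 30.7% / 29.9% |
| 60 | 1.179 / 1.217 | 29.7% / 28.7% |

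**4. False qualification at a true RDC of 35%.** For normal differences with correlation ρ, the squares have correlation about ρ². If r = 0.25 is on the differences, the design effect is 1 + 2 × 0.0625 = 1.125. It is 1.5 only if r is on the squares, which means differences correlated 0.5. Simulated with N df and 30 completers:

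- no correlation: 4.2% / 2.1%
- r on the differences: about 5% / 2.6%
- r on the squared relative differences: about 7.7% / 4.5%

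With 40 completers the last two are 4.5% / 2.3% and 7.1% / 4.3%.

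**5. Planned scenarios.** The chi-square bounds with N and N/1.5 df disagree in 0.1–1.5% / 0.3–3.7% of trials with 40 completers, and in at most 4.1% / 7.5% with 30.

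**6. Candidate bounds, true RDC 35%, 30 and 40 completers.**

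- N/1.5 df: 1.5–3.9% / 0.5–1.9%, conservative throughout.
- Plain percentile subject bootstrap: 6.5–9.4% / 4.1–6.4%, anti-conservative.
- Subject-level bootstrap-t on the log scale, differences correlated 0.25 or 0.5: 4.2–5.0% / 2.1–2.9% in one simulation (2,500 trials × 1,000 resamples) and 4.6–6.0% / 2.2–3.4% in a repeat (4,000 × 1,000). Close to nominal without an assumed r.

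**7. Power in the worst scenario (23, 25, 25, 27, 30%), squares correlated 0.25, 30 completers.** N df 96% / 93%; N/1.5 df 92% / 85%; bootstrap-t (same 4,000 × 1,000 simulation) about 83% / 73%. With 40 completers bootstrap-t gives about 91% / 84%. If r is on the differences, bootstrap-t with 30 completers gives about 92% / 86%.

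**The case against.** The best defence is that little turns on this at the planned values: the pooled endpoint has ample power under either tail, and step 5 shows that the degrees of freedom seldom change the decision. That stands for the clustering point. It does not answer the tail conflict, because the VCTE claim of 80% power fails at the 2.5% point.

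A reader might infer that the pooled bound is shown to qualify poor biomarkers 1.5 to 1.8 times too often. The documents do not support that. The excess needs r = 0.25 to describe squared relative differences, and 9.2 says only that observations are correlated. On the other reading there is no excess.

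A reader might also infer that the deciding bound is open to choice after the data are seen. That goes too far. Section 9.4.2 gives a formula for the 95% upper bound, calls the bootstrap an additional CI, and then decides on the upper bound. The wording leans to chi-square. What remains is that the bound it leans to is the one that ignores clustering.

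Finally, the α of 0.95 might be taken to mean that estimates above 35% were intended to pass. The table in 9.2 rules this out, since it reproduces with a lower-tail percentile. It is a notation fault. The synopsis also speaks of automatic qualification, so a miss is not stated to be exclusion.

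**Conclusion.** The tail conflict is established from the plan's own figures and needs no assumption about r. The pooled table uses the 2.5% point and the VCTE size the 5% point. Under a single 2.5% rule, VCTE power at 32 is about 69%, not 80%; under a single 5% rule, the tabulated sizes give about 89–90%, not 80%. Section wording is split in the same way.

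The clustering mismatch between 9.2 and 9.4.2 is real but secondary. Its harm depends on what r correlates: from none to about 7.7% / 4.5% against nominal 5% / 2.5%. These figures assume normal measurements, three evaluable pairs per subject, 30 completers and a true RDC of 35%. The point should be fixed; it does not threaten the design.

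**What to change.** Before the data are seen:

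1. State one tail. Write the percentile in 9.4.2 as the lower 2.5% or lower 5% point, and use the same rule in 1.1, 4.1, 9.2 and 9.4.2 (and in 9.4.3, which repeats the percentile). Restate the figures to match. At the 2.5% point, 32 VCTE subjects give about 69% power, and 80% needs about 40, the whole planned enrolment. At the 5% point, the pooled table gives about 89–90%.
2. Name one bound that accounts for clustering as deciding for the pooled RDC. The subject-level bootstrap is preferable, because it is already planned and needs no assumed r. Its variant must be specified, for example bootstrap-t on the log scale rather than plain percentile. Report the N-df chi-square bound as supportive.
3. Alternatively, use chi-square with N/[1+(s−1)r] degrees of freedom, where s is the mean number of evaluable pairs per subject. State that r = 0.25 applies to squared relative differences, or use 0.0625 in both sections if the differences were meant. This bound depends on an assumed r and is conservative if the true correlation is lower.

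The cost is SAP wording and a few lines of analysis, with no new data. The passing estimate may fall by about one point (step 3). Worst-scenario power with 30 completers stays above 80% under the effective-df version (about 92% / 85%). Bootstrap-t costs more: about 83% at the 5% point, but about 73% at the 2.5% point if clustering is as strong as the factor 1.5 implies. Choose the tail and the variant together.

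### The formula for the primary 95% upper bound uses the wrong chi-square tail: as written it gives a lower bound, and the 35% rule passes about 95% of the time at a true RDC of 35%

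*Combined protocol and SAP*

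**What the plan says.** Section 9.2 sets the null hypothesis at an RDC of 35% or more and sizes the study on the upper 95% bound falling below 35%. The Synopsis (1.1) makes automatic advancement to Stage 2 depend on "an upper bound of the 95% confidence interval (CI) of the reproducibility coefficient less than 35" percent.

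Section 9.4.2 gives the bound as the estimated RDC times √(N/χ²_{N,α}). It defines χ²_{N,α} as the α-th "percentile of the chi square distribution with N degrees of freedom and α is 0.95". A subject-level bootstrap 95% CI is to be constructed as well. If the upper bound is under 35%, "then it will be concluded that the biomarker meets the prespecified precision criterion". The sentence does not say whether the chi-square or the bootstrap limit is meant.

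Section 9.4.3 repeats the chi-square expression and the value 0.95 for the per-scanner repeatability and reproducibility coefficients and the between-scanner coefficient.

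**The concern.** Under the plan's model, N × (estimated RDC)² / (true RDC)² follows a chi-square distribution with N degrees of freedom. An upper limit for the true RDC therefore needs a small divisor, taken from the lower tail: the 5th percentile for a one-sided 95% bound, or the 2.5th for the upper limit of a two-sided 95% CI. Dividing by the 95th percentile gives the lower limit instead.

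The result is used as a pass/fail rule. Followed literally, a biomarker whose observed RDC is already worse than 35% can be declared precise enough and advance automatically. The test of the null hypothesis in Section 9.2 is then reversed: instead of having to show an RDC below 35%, a biomarker fails only when the data show it to be above 35%.

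**Working it through.** **Inputs.** α = 0.95, N degrees of freedom and the 35% limit (9.4.2). Three ultrasound scanners per participant, 40 participants, within-subject correlation 0.25 and up to 25% loss (4.1, 9.2). Stated sizes: 40, 45, 50 and 55 independent observations for the four pooled scenarios, and 32 subjects for VCTE at an RDC of 25% (9.2).

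**Formulas.** Multiplier m = √(N/χ²_{N,q}), where q is the cumulative probability. Largest passing estimate = 35/m. Pass probability at true RDC θ = F_N[(35/θ)² × χ²_{N,q}], where F_N is the chi-square distribution function.

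**1. Can the literal formula have produced the plan's sample sizes?** Power at the stated sizes, by simulating two normal readings per observation with the 9.4.2 estimator:

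| Stated size | q = 0.025 | q = 0.05 | q = 0.95 (as written) |
|---|---|---|---|
| Pooled, 40 | 79.8% | 89.0% | 100% |
| Pooled, 45 | 80.5% | 89.3% | 100% |
| Pooled, 50 | 80.1% | 88.8% | 100% |
| Pooled, 55 | 81.5% | 89.7% | 100% |
| VCTE, 32 | 69.1% | 81.0% | 100% |

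The pooled table matches the 2.5th percentile and the VCTE size matches the 5th. As written, the formula would need only one observation for 80% power at an RDC of 25%, so it cannot be what was simulated.

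**2. The bound as written, without loss.** N = 40 × 3 = 120 for pooled ultrasound. For VCTE, N = 40 assumes that the same formula applies with one pair of readings per participant, because 9.4.2 writes out the estimator only for the five scanners.

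| | χ²_{N,q} | m | Largest passing estimate | Pass at true 35% | Pass at true 40% |
|---|---|---|---|---|---|
| N = 120, q = 0.95 | 146.57 | 0.905 | 38.7% | 95% | 31.9% |
| N = 120, q = 0.05 | 95.70 | 1.120 | 31.3% | 5% | 0.02% |
| N = 120, q = 0.025 | 91.57 | 1.145 | 30.6% | 2.5% | 0.01% |
| N = 40, q = 0.95 | 55.76 | 0.847 | 41.3% | 95% | 64.4% |
| N = 40, q = 0.05 | 26.51 | 1.228 | 28.5% | 5% | 0.4% |
| N = 40, q = 0.025 | 24.43 | 1.280 | 27.4% | 2.5% | 0.2% |

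For example, an observed pooled RDC of 38% gives 38 × 0.905 = 34.4% and passes.

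**3. With 25% loss.** N = 30 × 3 = 90 pooled and 30 for VCTE. As written, the multipliers are 0.892 and 0.828, the largest passing estimates are 39.2% and 42.3%, and the pass probabilities at a true RDC of 40% are 42% and 70%. At a true RDC of 35% the pass probability stays at 95% for any N.

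**4. Relaxing the chi-square model at a true RDC of 35%.** Simulated pass probability as written:

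- ratio estimator of 9.4.2, independent observations: 92% to 93% (N = 40 to 120);
- squared differences correlated 0.25 within subject (design effect 1.5): 91%;
- both together: 88%.

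**The case against.** The strongest reply is that this is a slip of notation. In upper-tail notation, χ² with subscript 0.95 is the 5th percentile. The text calls the quantity an upper bound throughout, the sizing was plainly done with lower-tail percentiles, and a bound below its own estimate would probably be noticed in the output. That is likely what was intended, and the 95% figure describes the sentence as written, not how the design was simulated. But the text says percentile, which fixes the lower-tail cumulative meaning, and a standard quantile call with 0.95 returns the wrong value. Section 9.4.3 repeats the wording, so the plan nowhere states the formula correctly. Correcting it after the results are seen would be a post hoc change to the pass/fail rule.

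The second reply is that the bootstrap limit does not share the error. This is true, and the decision sentence is ambiguous. The bootstrap CI is introduced only as an addition, however, and the chi-square expression is the only quantity given a formula and labelled the 95% upper bound. The error rate above therefore applies if the chi-square bound decides.

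Three smaller points stand. The exact 95% rests on independent observations and an exact chi-square distribution. The correct comparator is not settled, because the two sizings use different percentiles. Section 9.4.3 has no pass/fail rule, so the error there misreports bounds but does not create a false qualification.

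**Conclusion.** The concern holds. As written, the 95% upper bound is a one-sided 95% lower bound. If it decides, the 35% rule passes a biomarker whose true RDC is exactly 35% with probability 95% under the plan's model, or 88% to 93% allowing for the ratio estimator, clustering or both. The intended rate is 5% or 2.5%. At a true RDC of 40% it still passes 32% (pooled, N = 120) to 64% (VCTE, N = 40) of the time without loss, where a correct bound passes less than 1%. This must be corrected before analysis because the rule governs automatic advancement to Stage 2. The conclusion rests on reading percentile in its ordinary sense and on the chi-square bound being the deciding one. The VCTE figures also assume that the 9.4.2 formula is carried over to that endpoint.

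**What to change.** - In 9.4.2 and 9.4.3, delete the statement that α is 0.95 and define the divisor as an explicit lower-tail percentile: 0.05 for a one-sided 95% bound, or 0.025 for the upper limit of a two-sided 95% CI.
- Choose one and use the same wording in 1.1, 4.1, 9.2 and 9.4.2. The pooled table matches 0.025 and the VCTE size matches 0.05. Choosing 0.025 lowers VCTE power at 32 subjects and an RDC of 25% to 69% by simulation (71% by formula).
- State which limit decides. Even with the right tail, the chi-square bound with N degrees of freedom ignores clustering. With three observations per subject, correlation 0.25 and the chi-square model otherwise intact, simulated type I error is about 9% (5th percentile) or 5.5% (2.5th). For the pooled endpoint, the subject-level bootstrap or an effective number of degrees of freedom should decide.
- State that the bound also applies to VCTE, with its own N.

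The cost is a wording change in two sections, some alignment elsewhere, and no new data or participants. It should be made before any results are seen.
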